## **Table of Contents**

- 1. BACKGROUND
- 2. AIMS
- 3. STUDY DESIGN
- 4. ENDPOINTS
  - 4.1 Primary
  - 4.2 Secondary
  - 4.3 Tertiary
- 5. RANDOMIZATION
  - 5.1 Method of Randomization
  - 5.2 Allocation Concealment
- 6. SAMPLE SIZE
  - 6.1 Preliminary Data
  - 6.2 Sample Size Determination for Primary Outcome
  - 6.3 Power for Secondary Outcomes
  - 6.4 Power for Tertiary Outcomes
- 7. INTERIM MONITORING PLAN
  - 7.1 Overview
  - 7.2 Trial Adaptation Guidelines
  - 7.3 Monitoring Inter-practice Variation
  - 7.4 Monitoring of Efficacy and Futility
  - 7.5 Monitoring of Safety
- 8. ANALYTICAL PLAN
  - 8.1 Overview
  - 8.2 Comparability of Treatment Groups
  - 8.3 Analysis of Primary Outcome
  - 8.4 Analysis of Secondary and Tertiary Outcomes

Title	Mindfulness-Oriented Recovery Enhancement for Opioid Misuse and Chronic Pain in Primary Care: A Randomized Controlled Trial
Study Design	The design is a parallel group superiority trial. The unit of randomization is the individual patient.
Study Duration	5 years.
Trial Sites	University of Utah Health – Community Physicians Group.
Objective	Conduct a randomized controlled trial to determine the efficacy of a Mindfulness-Oriented Recovery Enhancement intervention for opioid misuse and chronic pain in primary care.
Number of Subjects	The target sample size is 260 participants enrolled (200 + oversampling by 30% for attrition) to provide 80% probability that a two-sided 95% confidence interval will have a margin (half-width) less than +/18 standard deviation for the between-groups difference in the study outcomes.
Main Inclusion Criteria	Age ≥18 with a chronic pain-related diagnosis, reporting current pain ≥3 on a 0-10 scale, currently taking prescription opioids for ≥3 months, and surpassed a validated cutpoint for opioid misuse on the Current Opioid Misuse Measure (COMM).
Intervention	Mindfulness-Oriented Recovery Enhancement (MORE) is a group behavioral intervention that unites mindfulness training, cognitive reappraisal, and positive psychological principles into an integrative intervention strategy targeting mechanisms of pain and opioid misuse.
Duration of Intervention	8 weeks.
Primary Outcome	The primary outcome is opioid misuse measured by the Drug Misuse Index, operationalized as scores on the COMM and triangulated by blinded clinical interview and urine drug screen. The co-primary outcome is chronic pain symptomology, operationalized as pain severity and functional interference scores on the Brief Pain Inventory (BPI).

Primary Analysis	Effects of treatment on the DMI will be analyzed with generalized mixed effects models, and effects on the BPI will be analyzed with mixed effect ANCOVA models, adjusting for baseline levels.
Secondary Outcomes	Opioid dose, psychological distress, and opioid craving.
Interim Analysis	Interim monitoring will focus on patient accrual, baseline comparability of treatment groups, protocol adherence, data completeness and quality, and safety. No interim outcome analysis is planned.

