## 3. STUDY DESIGN

A two-arm parallel RCT design with an active control group will minimize internal threats to validity. Mindfulness-Oriented Recovery Enhancement (MORE; n=130) and the Supportive Group Psychotherapy control (SG; n=130) will be equated for time spent in treatment. Assessors will be blind to treatment condition. Target sample sizes were determined via power and precision analyses. The unit of randomization is the individual patient. The co-primary outcomes are opioid misuse and chronic pain symptoms. Participants will complete a clinical assessment battery at pre- and post-treatment, and at 3-, 6-, and 9-month follow-ups. Participants will complete a psychophysiological assessment protocol at pre- and post-treatment. Participants will complete ecological momentary assessments (EMAs) of symptoms, skill practice, and opioid use during treatment and 1 month afterward up to 3 times/day (morning, noon, and night).

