## 6.2 Sample Size Determination

The table indicates the smallest detectable effects for a treatment X time interaction term given different sample sizes, assuming a Type I error rate of .05 and varying correlations between repeated measures, which ranged from .34 -.56 per outcome in the R03. Cohen defined f=0.10 and f=0.25 as small and medium effects, respectively. Thus our target N of 260 (N=200 + oversampling by 30% for attrition) will allow us to detect small-to-medium effects on continuous outcomes. Based on dichotomous clinical classification of opioid misuse data from the R03 (68% improvement for MORE versus 32% for SG), the proposed sample size will offer outstanding power (>.99) to detect differences of this magnitude on this outcome. (b) *Precision* of parameter estimation. Our target N will allow model parameters to be estimated with a high degree of precision. A per group sample size of N=130 provides 80% probability that a twosided 95% confidence interval will have a margin (half-width) less than +/- .18 standard deviation. Thus the proposed sample will provide precision more than adequate for estimating small clinical effects with high confidence. (c) *Multivariate models*. Generally, structural equation power calculations for the full information maximum likelihood sensitivity analyses can be based on Root Mean Square Error of Approximation (RMSEA) comparisons of nested models. The proposed sample provides, in a realistic testing scenario, greater than 80% power in a 1 df test (26 versus 25) of close fit comparing two models with RMSEA of .06 and .05 at  $\alpha$ =.05. These calculations are conservative. Maximum likelihood techniques retain all observations at all times, and efficiently incorporate correlated observations to yield an Effective Sample Size that is quantifiably larger than the number of subjects. With fully specified repeated dimensions, the anticipated correlations will yield an effective sample size that is 40% larger, or roughly N=360.

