**Table 2. Sample Size Estimates** 

Minimally detectable effect sizes (Cohen's f) for								
treatment X time interaction (pre-tx, post-tx, follow-up)								
Correlation	N = 100	N = 110	N = 120	N = 130				
0.25	0.16	0.15	0.14	0.14				
0.50	0.13	0.12	0.12	0.11				
0.75	0.09	0.09	0.08	0.08				

Due to COVID-19 and related research restrictions at the University of Utah, recruitment ended on March 31, 2020, with a total of 250 participants enrolled (10 participants less than the originally anticipated target N).

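### The .18 SD precision is quoted at the full 130 per group, with no attrition removed and no update at 250 enrolled, and it does not describe the between-groups difference the synopsis names

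*SAP*

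**What the plan says.** The synopsis (Number of Subjects) sets the target at 260 enrolled, derived as "200 + oversampling by 30% for attrition", and gives as the purpose of that number an 80% chance that a two-sided 95% interval for the between-groups difference has a half-width under .18 SD. Section 6.2 repeats the derivation: "our target N of 260 (N=200 + oversampling by 30% for attrition". Section 3 splits the 260 evenly: "Mindfulness-Oriented Recovery Enhancement (MORE; n=130) and the Supportive Group Psychotherapy control (SG; n=130" each.

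Under item (b), section 6.2 states the precision at 130 per group, with the same 80% probability and the same .18 SD, but does not say which quantity the interval is for. The closing note under Table 2 records that "recruitment ended on March 31, 2020, with a total of 250 participants enrolled", 10 short of target. No power or precision figure is restated after that note. The only percentage that the SAP links to attrition is the 30% oversampling, and no expected attrition rate is given.

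**The concern.** The plan sets aside 60 of the 260 participants for attrition and then quotes its precision as if all 260 were analysed. If 200 is the number the plan expects to keep, the precision belongs at 100 per group. With 250 enrolled, even zero loss gives 125 per group, so the stated basis of 130 can no longer occur.

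The synopsis also names the difference between groups as the target of the interval. With equal groups, the standard error of a difference is √2 times that of one group's mean, so one figure cannot serve both. A reader who relies on the synopsis would expect the treatment contrast to be estimated considerably more tightly than the stated sample supports without further modelling. Section 6.2 builds on this figure when it calls the precision more than adequate for small clinical effects.

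**Working it through.** **Inputs from the SAP.** Base 200, oversampling 30%, target 260 (synopsis; section 6.2). 130 per arm (section 3). 250 enrolled (note under Table 2). Two-sided 95% interval, 80% probability, half-width .18 SD (synopsis; section 6.2).

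**Step 1: the enrolment target.** 200 × 1.30 = 260, as stated. The loss that still leaves 200 is 1 − 200/N:

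- N = 260: 60/260 = 23.1%
- N = 250: 50/250 = 20.0%

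**Step 2: reproduce the .18.** In SD units, the half-width that is not exceeded with 80% probability is

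- one group mean: h = t(.975, n−1) × √(1/n) × √(χ²(.80, n−1)/(n−1))
- difference of two means: h = t(.975, 2n−2) × √(2/n) × √(χ²(.80, 2n−2)/(2n−2))

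where n is the number per group. At n = 130:

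- one mean: 1.9785 × 0.0877 × 1.050 = 0.182
- difference: 1.9692 × 0.1240 × 1.036 = 0.253

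The SAP's figure is matched, to two decimals, by the single-group mean. For the difference, 260 per group would give 0.177, but that is twice the planned arm size.

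**Step 3: the numbers enrolled and retained.**

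| Per group | Meaning | One group mean | Between-groups difference |
|---|---|---|---|
| 130 | 260 enrolled, no loss | 0.182 | 0.253 |
| 125 | 250 enrolled, no loss | 0.186 | 0.258 |
| 100 | the SAP's base of 200 | 0.210 | 0.290 |

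Moving from 130 to 100 per group widens either interval by about 15% (0.290/0.253 = 1.15; 0.210/0.182 = 1.15). Moving from a single mean to a difference at 130 widens it by 39% (0.253/0.182 = 1.39). The second effect is the larger.

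**Step 4: do the other sample-size statements survive?** Section 6.2 says "68% improvement for MORE versus 32% for SG), the proposed sample size will offer outstanding power (>.99"). At 100 per arm the power for 68% versus 32% is 0.9996 at alpha .05 and 0.998 at alpha .0167. Even at 87 per arm, about what 250 enrolled would leave after a 30% loss (250 × 0.70 = 175), it is 0.9986 and 0.994. The minimum detectable f for the treatment-by-time interaction (two groups, three occasions, 80% power) reproduces Table 2 when that table's N is read as total N. On that reading, f at a total of 175 is 0.118, 0.096 and 0.068 for correlations .25, .50 and .75. Each is below every Table 2 value for the same correlation. Both statements stand.

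**The case against.** **A stronger reading that does not hold.** A reader might infer that the 260 is miscalculated: keeping 200 after a 30% loss takes 200/0.70 = 286, while 260 would leave 182 and 250 would leave 175. That arithmetic is right, but the SAP does not say that 30% are expected to drop out. It says "oversampling by 30% for attrition", and adding 30% to 200 gives 260 exactly. If the anticipated loss was about 23%, the target is right. A reader might also infer a material loss of power, such as a fall from 80% to 76% or 75%. No calculation in the SAP has 80% power at 200, and the SAP's own power statements survive at 175 (step 4 of the working).

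**Mixed models use partial follow-up.** Section 8.3 keeps every observation, so a participant who misses some visits still contributes. This stands, and it means 100 per group is somewhat pessimistic if 200 complete and others have partial data. It does not justify quoting 130, which assumes complete data on an enrolment that was never reached.

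**The primary analysis is more efficient than a raw difference.** It adjusts for baseline and averages four visits. As an illustration, take the correlations of .34 to .56 in section 6.2 and assume they are equal across all visits. Adjusting a single visit for baseline multiplies the half-width by √(1 − r²) = 0.940 to 0.828, giving 0.238 to 0.210 at 130 per group, still above .18. Averaging four adjusted visits multiplies it by √((1 + 3r)/4 − r²) = 0.624 to 0.597, giving 0.158 to 0.151 at 130 and 0.181 to 0.173 at 100. So the final interval for the pain outcomes may well be near or below .18 SD. But the SAP does not claim this basis for its figure, and this calculation does not return .18 at 130 per group. The objection limits the practical harm. It does not make the statement correct as written.

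**Conclusion.** The point holds as a reporting error in the precision statement. The .18 SD is quoted at full enrolment although the plan reserves 60 of 260 for attrition. It was left unchanged when enrolment closed at 250. It matches a single-group mean, not the between-groups difference that the synopsis names. For that difference the half-width is 0.253 at 130, 0.258 at 125 and 0.290 at 100 per group, which is 1.4 to 1.6 times the stated figure (0.253/.18 = 1.41; 0.290/.18 = 1.61).

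These values assume a continuous outcome, equal groups with a common SD, one occasion and no baseline adjustment. They also take 200 as the retained number, because the SAP gives no other. The oversampling arithmetic is not in error. The consequence is limited: no test, alpha level or estimand depends on the precision figure.

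**What to change.** - In the synopsis and section 6.2(b), restate the precision for the between-groups difference at the retained number: about 0.29 SD at 100 per group, and 0.26 SD at 125 per group if none of the 250 is lost. Say that this is for an unadjusted comparison at one occasion. If the baseline-adjusted four-visit average is meant instead, say so and give the correlation assumed.
- Add one sentence on attrition: the oversampling keeps 200 if loss is at most 23% of 260, or at most 20% of the 250 enrolled. State the expected attrition rate, and whether the 30% is an inflation factor or a dropout rate.
- Revisit the sentence in section 6.2 that calls the precision more than adequate for small effects, so that it fits the restated figure.
- Leave the binary power and the detectable-effect statements as they are.

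The cost is a few sentences of SAP text and a less favourable precision figure. No extra enrolment and no change of analysis is needed.

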## 8.3 Analysis of the Primary Outcomes

Effects of treatment on opioid misuse and chronic pain symptoms will be evaluated using linear and nonlinear mixed models with fixed effects consisting of a time factor and between-subjects treatment factor (MORE vs. SG), and will adjust for randomization imbalance by covarying baseline levels of the outcome. For the continuous pain symptom outcome measured by the

Brief Pain Inventory (BPI), the longitudinal trajectory for individual i on outcome j in treatment group g at post-randomization time t is modeled, under the full-rank parameterization, as

$$(1) \ \ y_{ijg,t>1} = a_{ijg} + \beta y_{ijg,t=1} + \mu_{jg,t>1} + \varepsilon_{ijg,t>1} \ \ , \ \ a_{ijg} \sim N(0,\psi_j) \ , \varepsilon_{ijg,t>1} \sim MVN(0,\Theta_j) \ ,$$

 $a_{ijg}$  is a random intercept with zero mean and variance  $\psi_i$ ,

 $\beta$  is the fixed regression coefficient of the post measures on pre-randomization baseline (time 1) score  $y_{ii\alpha,t}$ =1

 $\mu_{jg,t>1}$  are the post-randomization treatment arm means at times 2 through 5, conditioned on baseline, equivalent in this parameterization to distinct intercept terms

 $\mu_{jgt>1} = E(y_{ijg,t>1} \mid a_i, y_{ijg,t=1})$  for each group and time, and  $\epsilon_{ijg,t>1}$  are multivariate normal random error terms assumed to follow either an independent scaled diagonal or AR1 error structure, as determined by comparison of BIC model statistics.

Opioid misuse as measured by the Drug Misuse Index (DMI) is a dichotomous longitudinal variable Y, and we will evaluate treatment impact with a generalized linear mixed model specifying a binary distribution and logit link, with time t and group g as categorical factors and a random intercept  $\zeta_i$ :

$$\log(\pi_i / (1 - \pi_i)) = \alpha_g + \beta_t + \gamma_{gt} + \zeta_i$$

$$Y_{igt} \mid \zeta_i \sim Bernoulli(\pi_{igt}), \ \zeta_i \sim iid \ N(0, \psi)$$

For the opioid misuse outcome (Drug Misuse Index; DMI), it is not necessary to adjust for baseline differences, as all participants exhibited opioid misuse at baseline.

Our primary interest lies in estimating, for the BPI co-primary pain outcome j, the adjusted main effect, which represents the overall benefit of treatment across all four post-treatment measurement points conditional on baseline:

(2) 
$$\hat{\delta}_j = (1/4) \sum_{t=2}^{t=5} \hat{\mu}_{g=SG,t} - \hat{\mu}_{g=MORE,t}$$

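### The synopsis attaches a .18 SD margin to the between-groups difference, but 130 per group as stated gives .253 SD; .18 is what one arm's mean gives

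*SAP*

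**What the plan says.** The Number of Subjects row of the SAP synopsis sets the target at 260, that is 200 plus 30% for attrition. Its only stated reason is a precision target: 80% probability that a two-sided 95% confidence interval has a half-width below .18 "standard deviation for the between-groups difference in the study outcomes". (The figure appears there without its decimal point; section 6.2 makes the value clear, and nothing here rests on the misprint.)

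Section 6.2 repeats the target for each group: "N=130 provides 80% probability that a twosided 95% confidence interval will have a margin (half-width) less than +/- .18 standard deviation". The sentence before it says only "Our target N will allow model parameters to be estimated with a high degree of precision". No parameter, correlation or baseline adjustment is attached to the margin. Correlations do appear earlier in 6.2, but for Table 2: "varying correlations between repeated measures, which ranged from .34 -.56 per outcome in the R03".

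Table 2 gives the "smallest detectable effects for a treatment X time interaction term given different sample sizes, assuming a Type I error rate of .05", over three occasions (pre-treatment, post-treatment, follow-up).

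Section 8.3 defines the primary BPI effect as something else: the MORE versus SG difference averaged over four post-baseline occasions and conditional on baseline. It is a 1-df test at .05/3 = .0167. The model has a random intercept, with errors "assumed to follow either an independent scaled diagonal or AR1 error structure".

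**The concern.** A half-width of .18 SD for a difference between two groups of 130 looks too small. The standard error of such a difference is sqrt(2/130) = .124 SD, and 1.96 times that is already .243 before any assurance allowance. The margin is the synopsis's reason for the sample size and is likely to be carried into reports as the trial's precision. A reader cannot reproduce it for the quantity it names, and whether it is true depends on a contrast and correlations that the precision sentence leaves out.

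A lesser point is alignment. The only detectable effects given for continuous outcomes are for a three-occasion interaction at .05. The primary BPI test is a four-occasion average at .0167, so section 6.2 has no detectable effect for it.

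**Working it through.** **Inputs.** 95% two-sided interval, 80% assurance, 130 per group, margin .18 SD (synopsis; section 6.2). 100 per group is the 200 left after the planned attrition. Correlations .34 to .56 (section 6.2). Four post-baseline occasions, baseline as covariate, alpha .0167 (section 8.3). Enrolment closed at 250 (note under Table 2), about 125 per arm if evenly split.

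**Formula.** Half-width = t(.975, df) × sqrt(chi2(.80, df)/df) × SE, in SD units.

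**Step 1: what reproduces .18.** Mean of one arm, n = 130, df = 129, SE = 1/sqrt(130):
1.9785 × 1.0502 × .0877 = **.182**.

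**Step 2: the quantity the synopsis names, on the stated inputs.** SE = sqrt(2/n), df = 2n − 2.
- n = 130: 1.9692 × 1.0360 × .1240 = **.253**, which is .253/.18 = 1.41 times the stated margin
- n = 100: 1.9720 × 1.0409 × .1414 = **.290**
- n = 250 gives .1803 and n = 251 gives .1800, so .18 needs **251 per arm**

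At 130 per arm, the chance that a plain difference has a half-width under .18 is below 1e-9, against the stated 80%.

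**Step 3: adjusting one visit for baseline.** Multiply by sqrt(1 − r²). At n = 130, r = .34 gives .238 and r = .56 gives .210. Still above .18.

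**Step 4: the planned BPI contrast.** Multiply the step 2 value by sqrt(V), where V = w'Sw − (w'c)², w = 1/4 on each post occasion, S holds the post-to-post correlations and c the baseline-to-post correlations. Equal variances and complete data are assumed.

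With compound symmetry, V = (1 + 3ρ)/4 − ρ². At ρ = .34 this is .505 − .1156 = .3894; at ρ = .56 it is .670 − .3136 = .3564. Pure AR1 uses ρ to the power of the lag, with equal steps.

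| Structure | ρ | V | 130 per arm | 100 per arm |
|---|---|---|---|---|
| Compound symmetry | .34 | .3894 | .158 | .181 |
| Compound symmetry | .56 | .3564 | .151 | .173 |
| Pure AR1 | .34 | .3952 | .159 | .182 |
| Pure AR1 | .56 | .4780 | .175 | .201 |

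A random intercept plus AR1, with adjacent correlation .34 to .56, stays within .151 to .175 (130 per arm) and .173 to .201 (100 per arm).

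**Step 5: two correlations instead of one.** Section 6.2 does not say which pairs of occasions .34 to .56 describes. Let baseline-to-post (b) and post-to-post (p) differ within it, so V = (1 + 3p)/4 − b².
- b = .56, p = .34: V = .505 − .3136 = .1914; half-width at 130 per arm .111
- b = .34, p = .56: V = .670 − .1156 = .5544; half-width at 130 per arm .188

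**Step 6: Table 2.** A noncentral F with df1 = 2, df2 = 2(N − 2), lambda = 3N f²/(1 − rho), alpha .05, power .80 and N as the total reproduces all 12 cells. At N = 130 it gives .137, .112 and .079, printed as .14, .11 and .08. The table is correct for what it covers, but labels neither its power nor its N as a total.

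**Step 7: detectable BPI difference for the section 8.3 test.** MDE = (2.394 + .842) × sqrt(2V/n), for alpha .0167 and 80% power.
- One common correlation, V from .3564 to .4780: .240 to .278 SD at 130 per arm, .244 to .283 at 125, .273 to .316 at 100
- Correlations differing within .34 to .56, V from .1914 to .5544: about .18 to .30 SD at 130 per arm and .20 to .34 at 100

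**The case against.** The strongest reply is that a plain difference is the wrong benchmark. The synopsis itself says BPI is analysed by mixed-effects ANCOVA adjusting for baseline, section 8.3 averages four visits, and section 6.2 speaks of model parameters and quotes correlations nearby. For that contrast, at 130 per arm and one common correlation, .18 holds. This stands, and it limits the point: the margin has not been shown to be false for the planned BPI analysis. It does not rescue the text. Neither precision passage names that contrast, and the synopsis applies the margin to the study outcomes in general, which include the binary misuse index, where an SD margin has no direct meaning. The bound can also fail under unequal correlations, and mostly fails at 100 per arm.

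It is also fair to say that pure AR1 is a boundary case. The model always has a random intercept, and pure AR1 puts the baseline to last-visit correlation at .34^4 = .01 to .56^4 = .10, far below the quoted range. If every pair must lie within .34 to .56 under a random intercept plus AR1, the margin is about .151 to .167 at 130 per arm and .173 to .191 at 100. That trims the upper ends but leaves the pattern unchanged.

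On Table 2, the reply is right that the table is openly labelled and misstates nothing. The missing BPI line is an improvement, not an error. Section 6.2 does give power for the misuse outcome (above .99).

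A reader might infer that the trial is too small, or that a one-sample formula was used by mistake. The first does not follow: the planned contrast is much more precise than a plain difference. The second is suggested by the match at .182, but the SAP does not say how .18 was obtained.

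**Conclusion.** The concern holds as a misattributed precision figure. On the inputs the SAP states, the between-groups difference has a margin of .253 SD at 130 per arm and .290 at 100, not .18; the stated value agrees with the mean of one arm. For the planned four-visit, baseline-adjusted BPI contrast, .18 is met at 130 per arm under one common correlation (.151 to .175), is not assured if the two kinds of correlation differ (.11 to .19), and is mostly missed at 100 per arm (.173 to .201 under one common correlation). These ranges assume equal variances, complete data at the stated n, and correlations within .34 to .56. Because the likelihood analysis keeps partial records, 100 per arm is the cautious end if attrition is as planned. The arithmetic in steps 1 and 2 is certain; the ranges for the planned contrast are only as good as the correlations. Nothing here shows low power, and no planned analysis depends on the sentence. The Table 2 point is a secondary matter of alignment.

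**What to change.** In the synopsis and section 6.2, replace the .18 statement with the margin for the planned baseline-adjusted, four-visit BPI difference. State the baseline-to-post correlation, the post-to-post correlation and the error structure used, and give the margin at both 130 and 100 per arm. The trial team should supply the correlations; the ranges above are for orientation. If no adjustment is assumed, state .253 and .290 SD and say that they are for an unadjusted single-visit difference, which is not the planned analysis.

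As a secondary improvement, label Table 2 as total N at 80% power. Add one line with the detectable BPI difference for the section 8.3 contrast at alpha .0167 and 80% power, under the same stated correlations. With one common correlation it should come out near .24 to .28 SD at 125 to 130 per arm and .27 to .32 at 100; the wider ranges in step 7 apply if the correlations differ.

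The cost is one rewritten sentence in two places, two table labels and one added line. Enrolment, tests and alpha do not change.
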